### **Assessing Severity of Adverse Events**

Adverse events will be graded on a 5-point scale according to CTCAE v 4.03. Investigators will report CTCAE grades for all AEs (for both increasing and decreasing severity).

## Assessing Relationship to Study Treatment

Items to be considered when assessing the relationship of an AE to the study treatment are:

- Temporal relationship of the onset of the event to the initiation of the study treatment
- The course of the event, especially the effect of discontinuation of study treatment or reintroduction of study treatment, as applicable
- Whether the event is known to be associated with the study treatment or with other similar treatments
- The presence of risk factors in the study subject known to increase the occurrence of the event
- The presence of nonstudy, treatment-related factors that are known to be associated with the occurrence of the event

## Classification of Causality

Yes (related) A causal relationship between the study drug and the AE is a reasonable possibility.

No (not related) A causal relationship between the study drug and the AE is not a reasonable possibility.

### 9.5.1.5.2 SERIOUS ADVERSE EVENTS AND EVENTS ASSOCIATED WITH SPECIAL SITUATIONS

An SAE is any untoward medical occurrence that at any dose:

- Results in death
- Is life-threatening (ie, the subject was at immediate risk of death from the adverse event as it occurred; this does not include an event that, had it occurred in a more severe form or was allowed to continue, might have caused death)
- Requires inpatient hospitalization or prolongation of existing hospitalization
- Results in persistent or significant disability/incapacity
- Is a congenital anomaly/birth defect (in the child of a subject who was exposed to the study drug)

Other important medical events that may not be immediately life-threatening or result in death or hospitalization but, when based on appropriate medical judgment, may jeopardize the subject or may require intervention to prevent one of the outcomes in the definition of SAE listed above should also be considered SAEs. Medical and scientific judgment should be exercised in deciding whether expedited reporting is appropriate in such situations.

For this study, occurrence of T-cell lymphoblastic lymphoma/T-cell acute lymphoblastic leukemia or myeloid malignancy including myelodysplastic syndrome will be considered AEs of interest for this study. These events should be reported to the sponsor by completed SAE report (see [Section 9.5.4.3.2](#)) and considered as serious only if events meet the serious criteria. These AEs should be entered on the CRF even if the events do not meet serious criteria.

In addition to the above, events associated with special situations include pregnancy or exposure to study drug through breastfeeding; AEs associated with study drug overdose, misuse, abuse, or medication error (see [Section 9.5.4.2](#) and [9.5.4.3](#)). These events associated with special situations are to be captured using the SAE procedures but are to be considered as SAEs only if they meet one of the above criteria. All AEs associated with special situations are to be reported on the CRF whether or not they meet the criteria for SAEs.

All SAEs must be followed to resolution or, if resolution is unlikely, to stabilization.

The following hospitalizations are not considered to be SAEs because there is no “adverse event” associated with the hospitalization:

- Hospitalizations for respite care
- Planned hospitalizations required by the protocol
- Hospitalization planned before informed consent (where the condition requiring the hospitalization has not changed after study drug administration)
- Hospitalization for administration of study drug or insertion of access for administration of study drug
- Hospitalization for routine maintenance of a device (eg, battery replacement) that was in place before study entry

#### 9.5.1.5.3 LABORATORY MEASUREMENTS

Clinical laboratory tests to be performed, including hematology, chemistry, and urinalysis, are summarized in [Table 5](#). The Schedule of Procedures/Assessments ([Table 6](#)) shows the visits and time points at which blood for clinical laboratory tests and urine for urinalysis will be collected in the study. Clinical laboratory tests will be performed at each site.

**Table 5 Clinical Laboratory Tests**

Category	Parameters
Hematology	WBC count with differential (basophils, eosinophils, lymphocytes, monocytes, neutrophils), RBC count, hemoglobin, hematocrit, and platelets Peripheral blood smear morphology assessment a
Chemistry	
Liver function tests	AST, ALT, ALP, total bilirubin, direct bilirubin
Renal function tests	Creatinine, BUN
Other	Total protein, albumin, globulin, LDH, creatine phosphokinase, amylase, uric acid, glucose, triglycerides, cholesterol, INR, sodium, chloride, potassium, calcium, phosphorus
Urinalysis	Protein (qualitative), glucose (qualitative), occult blood

ALP = alkaline phosphatase, ALT = alanine aminotransferase, AST = aspartate aminotransferase, BUN = blood urea nitrogen, INR = international normalized ratio, LDH = lactate dehydrogenase.

a: On Day 15 of each cycle, peripheral blood smear morphology assessment can be omitted at the discretion of the investigator or subinvestigator, if there was no concern for safety of the subject. If peripheral blood smear morphology assessment is confirmed to be abnormal (eg, blood cell dysplasia, appearance of blast cells) and myeloid malignancy including myelodysplastic syndrome is suspected, then conduct bone marrow aspirate with cytogenetic testing (eg, G-banding).

For the management of clinically significant laboratory abnormalities, refer to the Tazemetostat Dose Reduction and Interruption Instructions in [Table 2](#). A laboratory abnormality may meet the criteria to qualify as an AE as described in this protocol (see [Section 9.5.1.5.1](#)). In these instances, the AE corresponding to the laboratory abnormality will be recorded on the CRF.

#### 9.5.1.5.4 VITAL SIGNS AND WEIGHT MEASUREMENTS

Vital sign measurements (ie, systolic and diastolic blood pressure [mmHg], pulse [beats per minute], temperature [in centigrade]), body weight (kg), and height (cm) will be obtained at the visits designated in the Schedule of Procedures/Assessments ([Table 6](#)) by a validated method. Blood pressure and pulse will be measured after the subject has rested.

#### 9.5.1.5.5 PHYSICAL EXAMINATIONS

Physical examinations will be performed as designated in the Schedule of Procedures/Assessments ([Table 6](#)). Documentation of the physical examination will be included in the source documentation at the site. Only changes from screening physical examination findings that meet the definition of an AE will be recorded on the CRF.

#### 9.5.1.5.6 ELECTROCARDIOGRAMS

ECGs will be obtained as designated in the Schedule of Procedures/Assessments ([Table 6](#)). Standardized, 12-lead ECG recordings that permit all 12 leads to be displayed on a single

page with an accompanying lead II rhythm strip below the customary 3×4 lead format are to be used. In addition to a rhythm strip, a minimum of 3 full complexes should be recorded from each lead simultaneously. ECGs will be obtained after the subject has rested.

ECG parameters (heart rate, PR interval, QRS interval, QRS axis, QT interval, QTcF interval, RR Interval) will be recorded on the CRF. ECG findings (normal, abnormal not clinically significant, abnormal clinically significant) will also be recorded. QTc will be corrected using Fridericia method (QTcF).

An ECG abnormality may meet the criteria of an AE as described in this protocol (see [Section 9.5.1.5.1](#)). In these instances, the AE corresponding to the ECG abnormality will be recorded on the CRF.

#### 9.5.1.5.7 OTHER SAFETY ASSESSMENTS

##### 9.5.1.5.7.1 Echocardiograms and MUGA scan

An echocardiogram or a MUGA scan (using technetium-99m-pertechnetate) to assess LVEF will be performed as designated in the Schedule of Procedures/Assessments ([Table 6](#)). Echocardiograms or MUGA scans and should be performed locally in accordance with the institution's standard practice. Either an echocardiogram or a MUGA scan which is used for an individual subject at baseline should be repeated for all subsequent LVEF assessments for that subject. LVEFs as assessed by the institution will be entered into the CRF.

##### 9.5.1.5.7.2 ECOG PS

An ECOG performance status (ECOG-PS) should be done at each visit as designated in the Schedule of Procedures/Assessments ([Table 6](#)).

##### 9.5.1.5.7.3 Pregnancy Test

An hCG or  $\beta$ -hCG test will be performed for women of childbearing potential. A serum or urine sample will be taken at visits as designated in the Schedule of Procedures/Assessments ([Table 6](#)).

All females will be considered to be of childbearing potential unless:

- Postmenopausal (amenorrheic for at least 12 consecutive months without other known or suspected cause)
- Sterilized surgically (bilateral tubal ligation at least 1 month before dosing, total hysterectomy, or bilateral oophorectomy at least 1 month before dosing).

##### 9.5.1.5.7.4 Viral Tests

Hepatitis B surface (HBs) antigen, HBs antibody, hepatitis B virus core (HBc) antibody, hepatitis C virus (HCV) antibody, and HIV antibody tests will be performed at Screening. When subjects have HBs antibody or HBc antibody positive results, HBV-DNA tests will be performed.

## 9.5.2 Schedule of Procedures/Assessments

### 9.5.2.1 Schedule of Procedures/Assessments of the Study

[Table 6](#) presents the schedule of procedures/assessments for the study.

**Table 6 Schedule of Procedures/Assessments in Study E7438-J081-106 (EZH-106)**

Phase	Pre-treatment		Treatment						Extension		Follow-up	
Period	Screening a	Baseline	Cycle 0	Cycle 1					Cycle 2 and later		Discontinuation	Final observation
Day	Within 28 days before administration	Within 3 days before administration	1	1 b	3	8 (±1)	15 (±1)	22 (±1)	1 (±3) c	15 (±3) n	(+7)	30 days after last dosing (+7) d
Informed Consent	X								[X] m			
Demographic data	X											
Inclusion/exclusion Criteria	X	X										
Medical history/Current medical condition	X											
Previous therapy	X											
Height	X											
Body weight	X	X		X		X	X	X	X	X	X	
Physical examination	X	X	X	X		X	X	X	X	X	X	X
Vital signs	X		X	X		X	X	X	X	X	X	X
ECOG-PS	X	X		X					X		X	
12-lead ECGs e	X		X	X			X		X	X	X	
Echocardiogram or MUGA scan f	X								[X]			
Pregnancy test (if applicable)	X										X	
Virus test	X											
Hematology o	X	X		X		X	X	X	X	X	X	X
Blood chemistry	X	X		X		X	X	X	X	X	X	X
Urinalysis	X	X		X		X	X	X	X	X	X	X
PK (blood) g			X		X	X	X	X	[X]			
PK (urine) h			X				X					
Tumor assessments (CT) i	X									[X]	X	
Bone marrow aspiration or biopsy j	X									[X]		
Tazemetostat administration k			X	Continuous 28-day cycle of tazemetostat twice daily.								
Archival tumor sample submission l				X								
Adverse events				From informed consent to final observation								

Concomitant drug/therapies	From informed consent to final observation
----------------------------	--

Note, [X]: In case to perform.

C#/D# = Cycle #/Day #, CR = complete response, CT = computed tomography, ECG = electrocardiogram, ECOG-PS = Eastern Cooperative Oncology Group-Performance Status, MUGA = multigated acquisition, PK = pharmacokinetics.

a: Screening assessments may be used as baseline assessments if performed within 3 days of the first administration of study drug.

b: To start C1D1 on Cycle 0 Days 4-9.

c: +1 day for C2D1.

d: When subject needs to receive other anti-tumor therapy due to deterioration of the disease within 30 days after the final study drug administration, final observation must be conducted before initiation of other anti-tumor therapy and the data within 7 days before next anti-tumor therapy can be used for final observation. .

e: 12-Lead ECGs on C0D1, C1D1, and C2D1 will be collected at pre-dose and 0.5-2 hours post dose of first administration.

f: Echocardiogram or MUGA scan will be performed at screening, every 16 weeks (ie, Day 1 of every 4 cycles [ $\pm$  1 week]) from C2D1. Additional assessments may be performed if clinically indicated.

g: Blood samples for PK analyses of tazemetostat and metabolites will be collected in C0D1 at predose, 0.5, 1, 2, 4, 6, 8, 10, 12, 24, 48 and 72 hours postdose; C1D3 and C1D8 at predose of first administration; C1D15 at predose of first administration, 0.5, 1, 2, 4, 6, 8, 10, and 12 hours postdose (postdose blood samples should be collected before the second administration of study drug); C1D22 and C2D1 predose of first administration.

h: Urine samples for PK analyses of tazemetostat will be collected in C0D1 at predose, 0-24, 24-48 and 48-72 hours postdose; C1D15 at 0-12 hours postdose of first administration.

i: The data of tumor assessments before informed consent within 28 days from study drug administration can be used as screening data if it meets the requirement of the protocol. Perform tumor assessment at screening, every 8 weeks [ $\pm$ 1 week] (starting at Cycle 1 Day 1) during Cycles 2-6, every 12 weeks [ $\pm$  1 week] starting at Cycle 7 and beyond, and discontinuation. The data within 28 days can be used as discontinuation data.

j: The data of bone marrow aspiration or biopsy before informed consent within 42 days from study drug administration can be used as screening data if it meets the requirement of the protocol. After the study drug dosing, perform bone marrow aspiration or biopsy if the result of screening was positive or unconfirmed and when to confirm CR as best of response or if clinically indicated.

k: Subjects should not take study drug before evaluations are performed (except tumor assessments and peripheral blood smear morphology assessment), unless specified.

l: Submit pre-study drug treated tumor sample to central laboratory before final observation, as far as possible.

m: Informed consent should be obtained before initiating the study or before entering the Extension Phase when Cycle 2 or later administrations will be continued.

n: In Cycle 13 or later, visits and assessments on Day 15 can be omitted at the discretion of the investigator or subinvestigator, if there was no concern for safety of the subject.

o: On Day 15 of each cycle, peripheral blood smear morphology assessment can be omitted at the discretion of the investigator or subinvestigator, if there was no concern for safety of the subject.

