#### 9.3.1 Inclusion Criteria

Subjects must meet all of the following criteria to be included in this study:

- (1) Patients with histological diagnosis of B-cell NHL (except transformed lymphoma) as follows:
  - Diffuse large B-cell lymphoma (DLBCL)
  - Follicular lymphoma (FL)
- (2) Patient who has measurable disease as below.
  - Lymph node or ex-nodal disease diagnosed by CT scan.
  - Clearly measurable in 2 orthogonal ways by CT scan.
  - $\geq 1.5$  cm in long axis or  $> 1.0$  cm in short axis, when long axis were  $< 1.5$  cm.
- (3) Patient who had previous therapy with systemic chemotherapy and/or antibody therapy and for which no standard therapy exists.
- (4) Patient who was PD or did not have response (complete response [CR] or partial response [PR]) in previous systemic therapy, or relapsed or progressed after previous systemic therapy.
- (5) Patient with Eastern Cooperative Oncology Group (ECOG) performance status of 0 to 1
- (6) Patient with life expectancy of  $\geq 3$  months from starting study drug administration.
- (7) Patient with adequate renal function:
  - Serum creatinine  $\leq 1.5 \times$  upper limit of normal (ULN)
- (8) Patient with adequate liver function:
  - Total bilirubin  $\leq 1.5 \times$  ULN
  - Aspartate aminotransferase (AST) and alanine aminotransferase (ALT)  $\leq 3.0 \times$  ULN
- (9) Patient with adequate bone marrow function:
  - (confirm 2 weeks or later from last administration of granulocyte colony-stimulating factor [G-CSF] and blood transfusion, if these are used)
  - Absolute neutrophil count  $\geq 1.5 \times 10^3 / \mu\text{L}$  ( $\geq 1.5 \times 10^9 / \text{L}$ )
  - Platelet count  $\geq 10.0 \times 10^4 / \mu\text{L}$
  - Hemoglobin  $\geq 9.0$  g/dL
- (10) Patient with left ventricular ejection fraction (LVEF)  $> 50\%$  on echocardiography or multiple gate acquisition (MUGA) scan.
- (11) Patient with time between prior anti-tumor therapy and first administration of study drug as below:
  - Cytotoxic chemotherapy – At least 3 weeks
  - Non-cytotoxic chemotherapy (eg, corticosteroids\*, small molecule inhibitor) – At least 2 weeks
  - Monoclonal antibody (ies) – At least 4 weeks

- Radiotherapy
    - At least 3 weeks from radiation therapy
    - At least 6 weeks from prior radioisotope therapy
  - Autologous hematopoietic stem cell transplantation – At least 6 months

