### 9.5.1.3 Efficacy Assessments

Tumor assessment will be performed by investigator or subinvestigator using “The Lugano Classification (CT-Based Response)” (Cheson, et al., 2014). Overall response and best overall response (BOR) (best response recorded at the designated visits during the study) will be assessed. Perform CT scans at Screening, every 8 weeks (starting at Cycle 1/Day 1) during Cycles 2-6, every 12 weeks starting at Cycle 7 (Cycle 7/Day 1) and beyond, and discontinuation.

A bone marrow aspiration or biopsy will be performed at screening for evaluation of bone marrow infiltration of tumor. After the study drug administration, perform bone marrow aspiration or biopsy if the result of screening was positive or unconfirmed and when to confirm CR as best of response or if clinically indicated.

Preliminary anti-tumor activity will be objective response rate (ORR) as defined by “The Lugano Classification (CT-Based Response)” (Cheson, et al., 2014). ORR is defined as the proportion of subjects who have a BOR of CR or PR.

Details of procedure of efficacy assessments will be provided in the Attachment “Overall response evaluation criteria” separately provided to each site.

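### The baseline CT may be 28 days old and predate the last chemotherapy, radiotherapy or corticosteroid, so earlier shrinkage could count towards ORR

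*Protocol*

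**What the plan says.** **Age of the baseline scan.** Protocol Table 6 (Section 9.5.2.1), footnote i: "The data of tumor assessments before informed consent within 28 days from study drug administration can be used as screening data". The footnote adds only that the data must satisfy the protocol's requirements. On lesions, inclusion 2 sets measurability and size, not timing. Table 6 schedules a pre-dose CT under Screening only; the Baseline visit within 3 days of dosing re-checks eligibility without a new scan.

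**Washouts (inclusion 11, Section 9.3.1).** The minimum gap before first dose depends on the class of treatment:
- For cytotoxic drugs it is 3 weeks.
- For corticosteroids and small molecules the entry reads "Non-cytotoxic chemotherapy (eg, corticosteroids\*, small molecule inhibitor) – At least 2 weeks".
- For antibodies it is 4 weeks.
- For radiation the entry reads "At least 3 weeks from radiation therapy"; radioisotopes need 6 weeks.
- For autologous transplant it is 6 months.

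The asterisk on corticosteroids permits up to 10 mg prednisolone daily, or equivalent, for lymphoma symptoms.

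**Ban on other anti-tumor therapy.** Section 9.4.7.1 starts it at enrollment, which can be later than the scan.

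**Use of the scan.** Section 9.5.1.3: "ORR is defined as the proportion of subjects who have a BOR of CR or PR". SAP 5.4 adds a waterfall plot of change in target-lesion size from baseline. SAP 8.2 takes the latest available pre-dose value as baseline, with no condition about prior therapy.

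**The concern.** The look-back for the reference scan is longer than some of the washouts. A patient could have a CT 28 days before first dose showing relapse, then have a node irradiated until Day -21 or take corticosteroid above the permitted level until Day -14, and still meet the stated timing rules. The first on-treatment CT would then measure the effect of that treatment together with tazemetostat.

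The study has a single arm, so nothing in the design can separate the two. Anti-tumor activity is a named secondary objective, and with about 6 subjects one misattributed response is a large share of the estimate.

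**Working it through.** The plan gives no figure to reproduce on this point: the sample size of 6 is stated not to rest on statistical considerations, and the documents give no misattribution rate. The check is a comparison of dates, followed by the effect of one subject on ORR.

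**1. Overlap.** Inputs: CT look-back of 28 days (footnote i) and minimum washouts (inclusion 11). Overlap = max(0, look-back − washout), the number of days after the oldest acceptable CT on which prior therapy may still be given.

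| Prior therapy | Minimum washout (days) | Overlap with 28-day CT (days) |
|---|---|---|
| Non-cytotoxic (corticosteroid, small molecule) | 14 | 28 − 14 = 14 |
| Cytotoxic chemotherapy | 21 | 28 − 21 = 7 |
| Radiotherapy | 21 | 28 − 21 = 7 |
| Monoclonal antibody | 28 | 28 − 28 = 0 |
| Radioisotope | 42 | 0 |
| Autologous transplant | 6 months | 0 |

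These are treatment days only; delayed shrinkage after the last dose would come on top.

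**2. Does another rule close the gap?** Inclusion 4 requires progression or lack of CR/PR in previous systemic therapy, or relapse or progression after it. That makes carry-over less likely after a systemic line on which the patient progressed. It leaves three openings:
- Stable disease, possibly with some shrinkage, qualifies.
- The criterion is tied neither to the most recent line nor to the CT date.
- Radiotherapy is not covered.

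**3. Effect of one subject on ORR.** With n = 6, one response is 1/6 = 16.7 points. Exact (Clopper–Pearson) 95% intervals:
- 1/6 = 16.7% (0.4 to 64.1)
- 2/6 = 33.3% (4.3 to 77.7)
- 3/6 = 50.0% (11.8 to 88.2)

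**4. How likely is at least one such case?** If each subject had an independent chance q of a misattributed response, P(at least one in 6) = 1 − (1 − q)^6. The values of q below are assumptions, chosen only to show the range.

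| q | P(at least one in 6) |
|---|---|
| 2% | 11% |
| 5% | 27% |
| 10% | 47% |
| 20% | 74% |

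**5. After the fix.** If the baseline CT must follow the last prior treatment, the overlap is 0 days for every class. At the minimum washout, the scan would be at most 21 days old after cytotoxic therapy or radiotherapy, and at most 14 days old after non-cytotoxic therapy.

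**The case against.** **Inclusion 4 and the Baseline eligibility check.** Systemic treatment given after the CT is itself previous systemic therapy, and eligibility is confirmed again within 3 days of dosing. This stands in part: it narrows the problem mainly to radiotherapy, short corticosteroid courses and stable disease with some shrinkage. It does not close it, for the reasons in step 2.

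**The response-criteria Attachment.** Section 9.5.1.3 refers procedural details to an Attachment that is not among the documents reviewed. It may contain a rule on scan timing or on irradiated lesions. This stands as a limit on the conclusion; if such a rule exists, footnote i needs only a cross-reference.

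**Antibody-based regimens.** Sections 7.1.3 and 7.1.5 describe rituximab-containing salvage treatment. Where a line ends with antibody, the 4-week washout equals the CT window and there is no overlap. This stands; a reader might infer that any prior therapy can follow the baseline scan, and inclusion 11 does not support that.

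**Direction of bias.** A reader might infer that ORR is necessarily inflated. That does not follow: in relapsed or refractory disease a tumor may grow between an old scan and first dose, which would hide later shrinkage. The net sign is unknown.

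**Bone marrow.** Footnote j says that "The data of bone marrow aspiration or biopsy before informed consent within 42 days from study drug administration can be used as screening data". That overlaps prior therapy by more (42 − 14 = 28, 42 − 21 = 21 and 42 − 28 = 14 days), and a reader might infer a larger effect on ORR. But ORR counts CR and PR alike, so an old marrow mainly affects the split between them. A rule forcing a repeat invasive procedure is not justified by ORR.

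**Materiality.** ORR is secondary and descriptive, with no hypothesis, and the intervals in step 3 overlap heavily. This bears on priority, not on whether the gap exists.

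**Conclusion.** The concern holds for the CT. As written, footnote i and inclusion 11 together allow cytotoxic chemotherapy or radiotherapy up to 7 days, and non-cytotoxic therapy up to 14 days, after the scan used as the efficacy baseline. Nothing in the supplied documents prevents shrinkage from that treatment being counted as response.

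One affected subject would move ORR by 16.7 points if 6 are analyzed; the step is smaller if replacement subjects enlarge the efficacy set. The frequency is not given and cannot be estimated from the documents. The conclusion assumes that the Attachment contains no timing rule.

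The documents do not show that any washout is wrong, that ORR will be biased upward on balance, or that the primary DLT endpoint is touched. This is a recommended, inexpensive correction to a secondary endpoint.

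**What to change.** **Protocol.** Add to Table 6 footnote i and Section 9.5.1.3: the CT used as the efficacy baseline must be obtained after the last dose or fraction of prior anti-tumor therapy, not counting corticosteroid at the level inclusion 11 permits. If the Attachment already says this, cross-refer to it instead. No washout changes.

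**SAP 5.4, for subjects already enrolled.** List the baseline CT date against the last prior-therapy date for every subject, and report ORR a second time with all affected subjects handled by one rule, for example excluded from both numerator and denominator. The rule must cover responders and non-responders alike, because removing affected responders only selects on the outcome and can only lower ORR. For illustration, from 3/6 (50.0%), excluding one affected responder gives 2/5 = 40.0%, and excluding one affected non-responder gives 3/5 = 60.0%.

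**Marrow.** No new requirement. At most, list the marrow date against the last prior therapy when a CR is reported.

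**Cost.** An occasional historical CT cannot be reused and the scheduled screening CT is done instead. Section 9.5.1.2.1 already collects chemotherapy end dates and last radiation dates, so the listing needs little new data. Corticosteroid given before consent may need a source check, because Section 9.4.7 records medication only from the consent date.
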